11.1.4.13. Incidence of QT prolongation

Incidence of QT prolongation will be analyzed separately. See separate document for the description of the analysis.

11.1.4.14. Analgesia, anesthesia and antibiotic use

For an analysis of the level of sedation, the number and percentage of patients per each level of sedation and each eschar removal procedure (in topical arms: 1st and second topical application, surgical rescue procedures and non-surgical rescue procedures; in SOC arms: surgical procedures and non-surgical procedures) will be tabulated.

The number of days of exposure to antibiotic drugs will be analyzed descriptively with number of units, number of missing values, mean, standard deviation, min, max, median and quartiles as shown in Table 4 and compared between groups with a one way analysis of variance. This analysis will be conducted for overall antibiotic use, for antibiotic use due to AE involvement (as indicated in the eCRF) and for prophylactic antibiotic use (as indicated in the eCRF) separately.

11.1.4.15. Hospital readmission rates

Hospital admission rates will be analyzed on a patient level by displaying counts and percentages by treatment group (see Table 5). The proportion of patients needing readmission to a hospital will be compared between treatment groups using a chi square test (or Fisher's exact test in case of small estimated cell counts) and presented graphically using bar plots.

Furthermore, the number of planned hospital readmissions per patient will be analyzed by displaying counts and percentages by treatment group (see Table 5). The number of planned hospital readmissions per patient will be compared between treatment groups using a chi square test (or Fisher's exact test in case of small estimated cell counts) and presented graphically using bar plots.

Additionally, the number of unplanned hospital readmissions per patient will be analyzed by displaying counts and percentages by treatment group (see Table 5). The number of unplanned hospital readmissions per patient will be compared between treatment groups using a chi square test (or Fisher's exact test in case of small estimated cell counts) and presented graphically using bar plots.

Hospital readmission will also be analyzed on a readmission level. Counts and percentages of planned/unplanned readmissions will be displayed by treatment group (see Table 5). The proportion of planned/unplanned readmissions to hospitals will be compared between treatment groups using a chi square test (or Fisher's exact test in case of small estimated cell counts) and presented graphically using bar plots

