2. Autografting can be reduced by selective debridement with increased preservation of uninjured dermis and potential for spontaneous epithelialization. In choosing the approach of epithelialization over preserved dermis, autografting is reserved to close full thickness wounds. In addition to the benefit of reduced surgery, decreased autografting reduces sacrifice of the subject's healthy uninjured skin and accompanying morbidity.
3. Blood loss is minimized by reduced excisional and autografting surgery.

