wound infection. At least one of the following histological signs of invasive burn wound infection is required:

- Microorganisms presence in viable unburned tissue
- Small vessel thrombosis and ischemic necrosis of unburned tissue
- Inflammation evident in unburned tissue
- Hemorrhage in uninjured tissue
- Evidence of microbial proliferation
- Variable migration of microorganisms along hair follicle and sweat glands
- Dense growth of nonviable-viable tissue interface (subeschar space)
- Intracellular viral inclusion
- Light microscopy
- Type A Cowdry bodies: herpes simplex virus-1
- Owl's eye inclusion bodies: cytomegalovirus
- Electron microscopy
- Intracellular virions

Vital signs (temperature, pulse, blood pressure and respiration rate) will be completed 24 hours prior to start of treatment and once daily from start of eschar removal until hospital discharge.

7.3.3.6. *Additional safety endpoints*

Additional safety endpoints to be evaluated in this study are:

- pain assessment (using VAS and as reported as AEs)
- units (and volume) of blood transfusion given during hospitalization
- Immunogenicity evaluation for NexoBrid patients
- Incidence of increased interstitial/compartment syndrome
- Incidence of QT prolongation
- Extent of analgesia, anaesthesia and antibiotic use
- Rates of hospital readmission
- Change in INR/PTT and incidence of change to > upper limit of normal (after treatment)
- Change in blood glucose and incidence of change to above upper limit of normal (after treatment)
- Long-term functionality evaluation of the extremities using the 'Lower Extremity Functional Scale'
- 'QuickDASH' questionnaires

- 'Range Of Motion' measurements
- Long-term Quality of Life using EQ5D and Burn Specific Health Scale- Brief (BSHS-B)

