9.3.1. Summary of sample size

Although the maximum sample size from the above calculations is a total of 121 patients (65 in the NexoBrid group, 13 in the Gel vehicle group and 43 in the SOC group (to match NexoBrid numbers)), we propose entering larger numbers to provide an extra margin of assurance in achieving positive results on the efficacy outcomes, and adequate information on safety outcomes to allow better benefit vs. risk assessment.

Therefore, we plan a study with total sample size of 175 patients; 75 (NexoBrid) + 75 (SOC) + 25 (Gel Vehicle).

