For each patient in the topical arms a binary (yes/no) variable is indicating whether the patient developed a burn-induced compartment syndrome (BICS) during the eschar removal procedure is given in the data.

Incidence of QT prolongation

Incidence of QT prolongation will be analyzed separately. The analysis and all needed transformations are described in a separate document.

Rates of hospital readmission

For each hospital readmission, a binary (yes/no) variable will be computed indicating whether this readmission was planned or not. A readmission will be considered as being planned when the reason for readmission was indicated as “planned wound management” or “scar modulation” in the eCRF. Readmissions for which the reason was given as “AE” in the eCRF are considered as being unplanned. Hospital readmission for which the reason is given as “other” will be reviewed by blinded personnel of the sponsor in order to decide whether they are to be classified as planned or unplanned.

For each patient a binary (yes/no) variable will be computed indicating whether this patient had a hospital readmission or not. Furthermore, a variable giving the number of planned hospital readmissions and a variable giving the number of unplanned readmissions will be computed for each patient.

Relative and absolute frequencies of hospital readmission will be calculated per treatment arm.

Change in PTT/INR

Change in PTT/INR will be computed as change from pre Eschar Removal procedure to 4h ± 15 min post first application (Topical arms) respectively to 4h post first SOC treatment (SOC arm) for each patient. Additionally, change from baseline PTT/INR will be computed for the first and second daily assessment post treatment (24h & 48h after start of debridement).

The proportion of patients with a change to > upper limit of normal range PTT/INR (patients with normal PTT/INR at baseline and PTT/INR > upper limit of normal range at the respective time point) will be computed per treatment arm and time point of measurement (4h post treatment, 24 h, 48h). Reference count is the number of patients with normal PTT/INR values at baseline. For the classification of normal and abnormal PTT/INR values, the reference limits of the local labs will be used.

Change in blood glucose

Change in blood glucose will be computed as change in blood glucose value from pre first topical procedure to 4h post first topical procedure (4h after removal of topical) and from

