Unless otherwise specified, all statistical tests will be conducted against a two-sided alternative hypothesis, employing a significance level of 0.05.

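### The supplementary readmission-level chi-square in SAP 11.1.4.15 tests the planned/unplanned mix among readmissions, not the readmission rate, and treats repeat readmissions of one patient as independent; keep the table and drop the p-value

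*SAP*

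**What the plan says.** The SAP lists "Rates of hospital readmission" among the additional safety endpoints in 7.3.3.6. Section 10.3.4.4 derives three patient-level variables: readmitted or not, number of planned readmissions, and number of unplanned readmissions. It also sets the classification: "A readmission will be considered as being planned when the reason for readmission was indicated as" planned wound management or scar modulation. Readmissions for an adverse event are unplanned, and those recorded as other are classified by blinded sponsor personnel.

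Section 11.1.4.15, under a heading about readmission rates, then plans four comparisons, each by chi-square or, with small expected counts, Fisher's exact test:

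1. Patients readmitted: "The proportion of patients needing readmission to a hospital will be compared between treatment groups using a chi square test".
2. Planned readmissions: "The number of planned hospital readmissions per patient will be compared between treatment groups using a chi square test".
3. Unplanned readmissions per patient, in the same way.
4. As an addition, with the readmission as unit: "The proportion of planned/unplanned readmissions to hospitals will be compared between treatment groups using a chi square test".

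The opening of Section 11 sets the general rule that "all statistical tests will be conducted against a two-sided alternative hypothesis, employing a significance level of 0.05", unless otherwise specified. The hierarchy in 11.1.8 contains only the primary endpoint and the three secondary efficacy endpoints.

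**The concern.** The first three comparisons have the patients of each arm behind them. The fourth does not. Its null hypothesis is that, among readmissions that occurred, the planned fraction is the same in each arm. Three things follow.

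- If one arm has proportionally more readmissions of both types, this null stays true. The test says nothing about the rate named in the section heading.
- If only planned readmissions fall and unplanned ones are unchanged, this null is false, and the arm with fewer planned readmissions shows the higher unplanned percentage. The p-value can then be significant although no extra unplanned readmission occurred.
- The chi-square takes every readmission as an independent observation. A patient readmitted several times contributes several correlated ones.

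At stake is the reading of one safety table. Its p-value would stand under a heading about rates, beside three that do concern patients, and the SAP does not say that it answers a different question.

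**Working it through.** **Inputs.** Arm sizes of 75 NexoBrid and 75 SOC come from SAP 9.3.1, and the two-sided 0.05 level from the opening of Section 11. The SAP gives no readmission rates, power or expected counts for this endpoint, so there is no figure of its own to reproduce. All readmission counts and rates below are assumptions.

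**Step 1: what the test sees.** For a 2×2 table of arm by type with cells a, b / c, d and total N, X² = N(ad − bc)² / (product of the four margins).

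| Readmissions, planned/unplanned | Unplanned share | X² | p |
|---|---|---|---|
| 12/8 vs 24/16 (both types doubled) | 40% vs 40% | 0 | 1.00 |
| 30/10 vs 15/10 (planned halved) | 25% vs 40% | 65 × 150² / (40 × 25 × 45 × 20) = 1.625 | 0.20 |
| 30/10 vs 10/10 (planned cut to a third) | 25% vs 50% | 60 × 200² / (40 × 20 × 40 × 20) = 3.75 | 0.053 |

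The first row is a doubling that the test cannot see. In the second and third rows the number of unplanned readmissions is identical, yet the unplanned share rises.

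**Step 2: the patient-level test beside it.** If the doubling means 12 of 75 versus 24 of 75 patients readmitted, X² = 150 × (12 × 51 − 63 × 24)² / (75 × 75 × 36 × 114) = 150 × 900² / 23,085,000 = 5.26, p = 0.022 (Fisher 0.035). By formula, power is 63% for 16% versus 32% of patients readmitted, and 77% for 20% versus 40%.

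**Step 3: simulation, 75 versus 75.** Poisson counts, 4,000 trials per scenario. SOC means per patient (planned/unplanned) were 0.12/0.08, 0.24/0.16, 0.30/0.10 and 0.40/0.20. The entries are the ranges of rejection rates over these four settings.

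| Scenario in NexoBrid | Readmission-level test | Any readmission, per patient | Unplanned count, per patient | Planned count, per patient |
|---|---|---|---|---|
| Both types doubled | about 5% | 55–89% | 20–49% | 29–79% |
| Planned halved, unplanned equal | 14–31% | 14–35% | about 4% | 17–49% |
| Planned cut to a third, unplanned equal | 26–59% | 22–58% | 3–5% | 33–83% |

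With higher assumed rates (unplanned 0.15–0.20; planned 0.4 to 0.2, or 0.6 to 0.3) and Poisson or overdispersed counts, the readmission-level test rejects in 26–38% when planned readmissions are halved. Almost all of those rejections show the higher unplanned share in NexoBrid.

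**Step 4: independence.** With no difference between arms and overdispersed (gamma-Poisson) counts, the readmission-level test rejects in about 9–11% of trials at a nominal 5%. Individual settings ran from 7% (gamma shape 1) to 12% (gamma shape 0.5), while the patient-level tests stay at about 5%. This needs a specific kind of clustering: planned and unplanned readmissions must vary between patients separately, so that one patient's readmissions tend to be of the same type. If a single patient factor multiplied both types equally, each readmission would still be planned with the same probability given the total, and the test would keep its level. The same type-specific clustering explains why its rejection rate under a doubling can reach 13–14%: that is inflation, not power.

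**The case against.** The strongest objection is that the section already holds the right analyses. Three patient-level comparisons come first, and the readmission-level one is introduced as an addition. A reader might infer that the plan misses a doubling of readmissions. The SAP does not support that: under the Poisson assumptions the planned any-readmission test rejects in 55–89% of trials in that case. This power falls when a few patients account for many readmissions, but that does not alter the reading of the plan.

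A reader might also infer that the test would declare NexoBrid worse. It would not. Tests are two-sided and no decision is attached to a higher unplanned share. If planned readmissions fall, the composition really has changed, so rejection correctly answers the question that the test asks. At the assumed rates, a halving of planned readmissions usually leaves the test non-significant, and the adjacent tests would show unplanned readmissions unchanged.

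Nor does the SAP equate planned readmission with regrafting. The Background says "Autografting can be reduced by selective debridement with increased preservation of uninjured dermis", but it does not mention readmission. A fall in planned readmissions under NexoBrid is therefore conceivable, not forecast.

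All of this stands and limits the point to one p-value. It does not defend that p-value: the test still sits under a heading about rates, measures something else, and assumes an independence that repeat readmissions may break.

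**Conclusion.** The point holds for the readmission-level chi-square alone. That test compares composition and not rate. It can be significant solely because planned readmissions fell, is uninformative when both types rise in proportion, and is anti-conservative (about 9–11% at a nominal 5%) when readmissions of the same type cluster within patients.

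The logic of the first three statements needs no assumption. Their size rests on assumed readmission rates, on assumed overdispersion, and on a two-arm comparison of NexoBrid with SOC, whereas the SAP speaks only of treatment groups.

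Severity is minor. This is an additional safety analysis outside the testing hierarchy, and the consequence is confined to how one table is reported and read.

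**What to change.** In SAP 11.1.4.15, delete the chi-square (and its Fisher alternative) at readmission level. Keep the counts and percentages of planned and unplanned readmissions by arm as a description, and label the table as the composition of readmissions. State that between-arm inference on readmission rests on the three patient-level comparisons already planned.

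Optionally, add a per-patient rate ratio with a 95% confidence interval for unplanned and, separately, planned readmissions, since the section now plans tests without an effect estimate. The choice of model for that is a preference, and the point does not depend on it.

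The cost is a few words in the SAP. The variables are already derived in 10.3.4.4, and no new data are needed.

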11.1.4.16. INR/PTT change

Change in INR/PTT will be evaluated at 4h post first treatment as well as on the first and second daily assessment post treatment separately. This is a binary (yes/no) variable indicating whether the patient experienced a change of INR/PTT to > normal range (reference limits of the local laboratories). Rates of patients with this event will be analyzed by displaying counts and percentages by treatment group (see Table 5) in each time point separately (4h post, 24h and 48h). Reference count is the number of patients with normal PTT/INR values at

baseline. For the classification of normal and abnormal PTT/INR values, the reference limits of the local labs will be used. The proportion of patients with change of INR/PTT to > normal range will be compared between treatment groups using a chi square test (or Fisher's exact test in case of small estimated cell counts).

INR/PTT values will be classified as normal, abnormal (NCS) and abnormal (CS) based in the eCRF. These will be analyzed by displaying counts and percentages by treatment group (see Table 5) for each time point separately (4h post, 24h and 48h).

11.1.4.17. *Blood glucose change*

This is a binary (yes/no) variable indicating whether the patient experienced a change of blood glucose to > upper limit of normal range. Rates of patients with this event will be analyzed by displaying counts and percentages by treatment group (see Table 5) per eschar removal procedure. Furthermore, bar plots will be displayed. The proportion of patients with change of blood glucose to > upper limit of normal range will be compared between treatment groups using a chi square test (or Fisher's exact test in case of small estimated cell counts).

Furthermore, the change in blood glucose from baseline to 4h post treatment per patient will be analyzed descriptively with number of units, number of missing values, mean, standard deviation, min, max, median and quartiles as shown in Table 4 and compared between groups with a one way analysis of variance. A graphical representation of the data will be done using histograms.

11.1.5. *Exploratory Analyses*

11.1.5.1. *% wound area surgically excised for eschar removal*

The % wound area surgically excised for eschar removal per patient (computed as in section 10.3.5.5) will be analyzed descriptively with number of units, number of missing values, mean, standard deviation, min, max, median and quartiles as shown in Table 4 and compared between groups with a one way analysis of variance. A graphical representation of the data will be done using histograms.

11.1.5.2. *Incidence of surgical Escharotomy procedures on circumferential extremities target wounds*

Two analyses will be done for this exploratory endpoint. The number and percentage of circumferential extremities target wounds that went through escharotomy will be presented by treatment group (see Table 5). The proportion of circumferential extremities target wounds that

went through escharotomy will be compared between treatment groups using a chi square test (or Fisher's exact test in case of small estimated cell counts).

The number and percentage of patients having at least one circumferential extremities target wound, which went through escharotomy, will be presented by treatment group (see Table 5). Furthermore, bar plots will be displayed. The proportion of patients having at least one circumferential extremities target wound which went through escharotomy will be compared between treatment groups using a chi square test (or Fisher's exact test in case of small estimated cell counts).

11.1.5.3. Incidence of reduction in interstitial/compartment pressure in circumferential extremities target wounds

This is a binary (yes/no) variable indicating whether the patient experienced reduction in interstitial/compartment pressure in circumferential extremities target wounds for each target wound and each procedure separately. Rates of patients with this event will be analyzed by displaying counts and percentages by treatment group (see Table 5). Furthermore, bar plots will be displayed. The proportion of patients with reduction in interstitial/compartment pressure in circumferential extremities target wounds will be compared between treatment groups using a chi square test (or Fisher's exact test in case of small estimated cell counts).

